12.12.3. Study Design

This is a multicenter sub-study of the main ASCEND-D study. Subjects who qualify for the main study will be assessed for enrolment. Approximately 136 subjects from centers in selected countries that are participating in the main study will be randomized.

Note: if the target number of randomized subjects in the ABPM sub-study is not achieved when the main study is fully enrolled, recruitment may be extended to allow randomization in the ABPM sub-study to complete.

12.12.3.1. ABPM Quality Control Criteria

Subjects will need to wear the ABPM device for two 24-hour sessions during the study: at a mid-week dialysis visit starting at Week -4 until 1 week prior to randomization (baseline ABPM) and then at Week 16. The ABPM device will be placed after assessments for the main study have been completed. Subjects will be expected to wear the ABPM device for 24 hours at each session. The ABPM device will measure BP and heart rate every 30 minutes during both awake and asleep hours. The times the subject awakens and goes to sleep during this 24 hour period will be recorded.

For each session the ABPM Quality Control (QC) criteria as defined in the Project Requirement Specification (PRS) for ABPM must be met. If these criteria are not met the ABPM may be repeated (see Section 12.12.3.3).

12.12.3.2. Eligibility Criteria – Screening

Additional Inclusion Criteria

In addition to meeting entry criteria for the main study, a subject will be eligible for inclusion in this sub-study only if all of the following criteria apply.

1. Signed written informed consent prior to beginning sub-study-related procedures.
Note: Consent to participate in this sub-study is separate from consent to participate in the main study, and will be signed either at Week -8 or at Week -4 prior to ABPM assessments.
2. Use of the same antihypertensive treatment for the 6 weeks prior to the Screening visit, through the entire Screening period and at randomization.
3. SBP of ≤ 170 mmHg based on the average of pre-dialysis clinic values obtained at Week -8 and Week -4 using the methodology described in the SRM.
4. Willing and able to wear ABPM device for 24 hours on two separate sessions.
5. Valid ABPM at baseline [**randomization (Day 1) only**].
6. Dialysis schedule of three times per week.
7. Average awake-time SBP of ≤ 150 mmHg as assessed by a valid baseline ABPM [**randomization (Day 1) only**].

Additional Exclusion Criteria

A subject will not be eligible for inclusion in this sub-study if any of the following criteria apply:

1. Receiving peritoneal dialysis or home HD.
2. Subjects who are at high risk for loss to follow-up (e.g., subjects who are known to not regularly attend dialysis, subjects who may require frequent hospitalizations or vascular access interventions).
3. Evidence of atrial fibrillation or atrial flutter at time of baseline ABPM assessment (see Section 12.12.3.3).
4. Oscillometer/sphygmomanometer cuff cannot accommodate their upper arm circumference.
5. BP cannot be measured in the arm opposite of current vascular access.
6. Subjects who experience, on average, >5% increase in weight above EDW between mid-week dialysis treatments between Week -8 and baseline ABPM reading.

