12.12.2. Objectives and Endpoints

Objectives	Endpoints
Primary	

 To compare daprodustat to rhEPO for effect on SBP (superiority) by ABPM in subjects receiving maintenance hemodialysis in the ABPM ITT population 	
 Change in 24 hour average SBP from baseline to end of sub-study¹ between treatment groups
Secondary	

 To assess the effect of daprodustat and rhEPO independently within treatment group on SBP, DBP and mean arterial blood pressure (MAP) by ABPM in the ABPM ITT population 	
 Change in 24 hour average SBP from baseline to end of sub-study¹ within each treatment group Change in 24 hour average DBP from baseline to end of sub-study¹ within each treatment group Change in 24 hour average MAP from baseline to end of sub-study¹ within each treatment group

 To compare the effect of daprodustat to rhEPO on DBP and MAP by ABPM in the ABPM ITT population 	
 Change in 24 hour average DBP from baseline to end of sub-study¹ between treatment groups Change in 24 hour average MAP from baseline to end of sub-study¹ between treatment groups

 To compare the effect of daprodustat to rhEPO on BP parameters in the ABPM per-protocol population 	
 Change in: 
 24 hour average SBP 24 hour average DBP 24 hour average mean arterial pressure from baseline to end of sub-study¹ between treatment groups

Objectives	Endpoints

 To assess the effect of daprodustat and rhEPO on BP parameters in the ABPM per-protocol population 	
 Change in: 
 24 hour average SBP 24 hour average DBP 24 hour average mean arterial pressure from baseline to end of sub-study¹ within each treatment group

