12.12.3.3. Study Assessments**Week -8 Study Visit:**

Subject's consent for ABPM is obtained (Note: if missed this may be obtained at Week -4 prior to ABPM assessments).

Week -4 Study Visit:

A baseline ABPM reading must be initiated at a mid-week dialysis visit and may be performed following completion of the Week -4 study assessments or at a subsequent mid-week dialysis visit provided it occurs at least 1 week prior to randomization.

Post-dialysis and prior to ABPM, subjects will be assessed for the presence of atrial fibrillation/flutter as follows: subjects with an irregular heart beat detected during heart rate measurement will undergo an ECG and those with documented atrial fibrillation or atrial flutter will not be eligible for ABPM.

The ABPM device will be placed on the arm opposite current vascular access, and will be removed by the subject at home after a minimum of 24 hours of wear; the device will be returned to the research staff at the next visit, which ideally is no later than 1 week prior to randomization to allow for QC of the ABPM. See SRM for guidance on placement of ABPM device.

If the subject fails to meet the baseline ABPM QC criteria and agrees to repeat the ABPM procedure, then:

- The baseline ABPM procedure can be repeated at the next mid-week dialysis visit. *Note: the atrial fibrillation/flutter assessment should be repeated prior to device placement.*
- Day 1 (randomization) may be delayed.
- If the baseline ABPM fails the QC criteria after three attempts, then the subject will not be enrolled in this ABPM sub-study.

Subjects will have their body weight measured and recorded in the eCRF both pre- and post-dialysis (see SRM for guidance on body weight measurement).

Day 1 (Randomization):

If the ABPM measurements meet the QC criteria, the subject can be randomized.

Subjects who either do not qualify for entry into the ABPM sub-study after failing QC criteria a third time or who do not desire to continue in the ABPM sub-study although they pass the QC criteria, should continue with randomization into the main study following the schedule of assessments as outlined in [Table 7](#) of the main protocol if appropriate.

Week 16 Study Visit:

At Week 16, at the mid-week dialysis visit and after all main study assessments have been completed, the subject's pre- and post-dialysis weight will be measured and the EDW will be recorded.

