12.12.4. Sample Size and Power Calculations

The sample size of this sub-study has been designed based on the primary sub-study objective to demonstrate superiority in average SBP change from baseline to end of sub-study between arms (daprodustat versus rhEPO), measured by ABPM over a 24 hour assessment period. Assuming a one-sided 2.5% significance level, a true standard deviation for SBP change from baseline measured by ABPM of 11 mmHg [Peixoto, 2000], and up to a 20% withdrawal rate from the sub-study, a sample size of 68 subjects per group (136 subjects in total) will provide greater than 80% power to detect a -6 mmHg difference in treatment groups (i.e., achieve superiority). Under these assumptions, superiority will be established if there is more than a 4.2 mmHg mean difference observed in favor of daprodustat.

Assuming a 40% screen failure rate for the additional ABPM entry criteria, approximately 228 subjects that are eligible for the main study will need to be screened for the sub-study in order to randomize approximately 136 subjects. See Section 9.2.3 for more information about sample size adjustments.

Unblinded ABPM data will be reviewed by the IDMC during the conduct of the trial as part of their data monitoring responsibilities. No formal interim analysis is planned.

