In order to contextualise the primary between-group comparison, a key secondary objective is to assess within-group changes from baseline over the sub-study. Assessment of within-group changes will support interpretation of the primary analysis by identifying whether there was an absence of an increase in BP in one or both treatment groups. To that end, two-sided 95% confidence intervals will be calculated for change from baseline in each ABPM parameter separately for each treatment group. For either treatment group, a lack of adverse effect on the primary endpoint of average SBP at end of sub-study will be concluded if the upper 95% confidence limit is no more than 4 mmHg. This margin was chosen as it is less than the clinically meaningful change of 5 mmHg [Whelton, 2002] and it is half the historical increase in SBP observed with rhEPO [Krapf, 2009].

The mean and two-sided 95% CI will be estimated from the primary statistical model for within treatment arm SBP change from baseline to end of sub-study.

The change from baseline 24 hour average DBP, mean arterial pressure and heart rate at end of sub-study will be assessed in a similar way as the primary, using analogous ANCOVA models with treatment and baseline as covariates.

The differences in proportion of subjects that increase/decrease their BP medication (number or dose) will be assessed using Fisher's Exact Test. The differences between treatment groups in the proportion of subjects that convert from dippers/non-dippers at baseline to non-dippers/dippers at end of sub-study will also be assessed using Fisher's Exact Test.

Plots of the mean 24 hour average values (two-sided 95% CIs) and mean changes from baseline in 24 hour average values (two-sided 95% CIs) for BP will be provided by treatment group.

Additional statistical considerations will be addressed in the RAP.

References

Agarwal R. Blood Pressure and Mortality Among Hemodialysis Patients. *Hypertension*. 2010; 55:762-768.

Peixoto AJ ,Santos SF, Mendes RB, Crowley ST, Maldonado R , Orias M, et al. Reproducibility of ambulatory blood pressure monitoring in hemodialysis patients. *Am J Kidney Dis*. 2000; 36: 983–990.

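### ABPM sub-study: the 150 mmHg entry limit is applied to the session that is also the baseline, so within-arm SBP change, and the 4 mmHg rule built on it, are biased upward

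*Protocol*

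**What the plan says.** All references are to Protocol Appendix 12.

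- **Entry limit (12.12.3.2).** Inclusion 7, checked at randomization, requires "Average awake-time SBP of ≤ 150 mmHg as assessed by a valid baseline ABPM". It has an upper bound and no lower bound. A separate limit of 170 mmHg applies to clinic SBP, "mmHg based on the average of pre-dialysis clinic values obtained at Week -8 and Week -4".
- **Number of sessions (12.12.3.1).** "Subjects will need to wear the ABPM device for two 24-hour sessions during the study": one before randomization and one at Week 16.
- **Repeats (12.12.3.3).** The baseline session may be redone "If the subject fails to meet the baseline ABPM QC criteria and agrees to repeat the ABPM procedure". No separate qualifying session is described.
- **Endpoints (12.12.2).** The primary is "Change in 24 hour average SBP from baseline to end of sub-study", compared between arms. A secondary objective is "To assess the effect of daprodustat and rhEPO independently within treatment group on SBP, DBP and mean arterial blood pressure (MAP").
- **Within-arm rule (12.12.5).** Within-arm change is called a key secondary objective that gives context to the primary result. For 24-hour SBP, absence of a harmful effect "will be concluded if the upper 95% confidence limit is no more than 4 mmHg". The mean and interval come from the primary ANCOVA, whose terms are treatment and baseline 24-hour SBP.
- **Screening loss (12.12.4).** "Assuming a 40% screen failure rate for the additional ABPM entry criteria". This covers all the sub-study criteria together; the share due to inclusion 7 is not given.

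**The concern.** One reading does two jobs. It decides who enters, and it is the value subtracted from the Week 16 reading. Subjects who happened to read low that day are kept and those who happened to read high are dropped, so the expected Week 16 value exceeds baseline in both arms even if neither drug changes BP.

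The baseline term in the ANCOVA does not remove this. By default the adjusted within-arm mean is evaluated at the average baseline of the selected subjects, and that average is the quantity that selection has pulled down.

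A between-arm difference cancels the shift. A statement about one arm against a fixed 4 mmHg limit does not. At stake is whether a neutral arm fails the rule and seems to show a BP rise, which would blur the context the within-arm analysis is meant to supply.

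**Working it through.** **Inputs from Section 12.12.4.** SD of change 11 mmHg; 68 per arm; up to 20% withdrawal, so 68 × 0.8 = 54.4, taken as 54; target difference 6 mmHg; one-sided 2.5%.

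**Reproducing the plan's figures.** n per arm = 2 × 11² × (1.960 + 0.842)² / 6² = 52.8, so 53; 53 / 0.8 = 66.3, so 67 (stated 68). Smallest winning difference = 1.983 × 11 × √(2/54) = 4.20 mmHg (stated 4.2). Screened = 136 / 0.6 = 227 (stated 228). The inputs are understood as the plan intends.

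**Room in the 4 mmHg rule.** SE = 11/√54 = 1.497; half-width = 2.006 × 1.497 = 3.00. The observed mean change must be 4 − 3.00 = 1.00 mmHg or less. With no withdrawals (68 per arm) the figure is 1.34.

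**Regression to the mean.** Assume no true change, normal readings and the same between-subject SD σ at both sessions, with correlation ρ. Then 2σ²(1 − ρ) = 11² = 121, so σ²(1 − ρ) = 60.5. If a share f is excluded at the top, and z is the normal quantile at 1 − f,

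expected rise = (60.5/σ) × φ(z)/(1 − f).

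Neither σ nor f is in the protocol. I assume σ = 13-20 mmHg and f = 2-30%. Example: f = 0.10 gives φ(z)/(1 − f) = 0.1755/0.90 = 0.195; at σ = 20 the rise is 3.025 × 0.195 = 0.59 mmHg.

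**Chance that a neutral arm meets the rule.** The specified estimate comes from the ANCOVA, so the residual SD applies: √(60.5 × (1 + ρ)), with ρ = 1 − 60.5/σ². For σ = 13, ρ = 0.642 and the residual SD is 9.97. For σ = 20, ρ = 0.849 and it is 10.58. With 54 per arm the SEs are 1.357 and 1.440, and the largest passing means are 4 − 1.983 × SE = 1.31 and 1.15 mmHg. Probabilities are from the noncentral t with 105 df.

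| Excluded by inclusion 7 | Rise, σ = 20 | Rise, σ = 13 | Rule met, σ = 20 | Rule met, σ = 13 |
|---|---|---|---|---|
| none | 0 | 0 | 0.786 | 0.832 |
| 2% | 0.15 | 0.23 | 0.755 | 0.786 |
| 5% | 0.33 | 0.51 | 0.715 | 0.723 |
| 10% | 0.59 | 0.91 | 0.651 | 0.618 |
| 20% | 1.06 | 1.63 | 0.526 | 0.410 |
| 30% | 1.50 | 2.31 | 0.405 | 0.234 |

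**Awake versus 24-hour SBP.** The limit is on awake SBP and the endpoint is 24-hour SBP from the same session, so the shift is somewhat smaller. With an assumed correlation of 0.95 between the two, simulation gives 2.20 instead of 2.31 mmHg (σ = 13, 30% excluded). With a cautious attenuation factor of 0.8, every rise in the table falls by a fifth.

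**Primary comparison.** In an ANCOVA simulation with 54 per arm, mean 140, σ = 20 and the limit applied, the within-arm mean was +1.54 mmHg with no true change. The between-arm difference was 0.01 and the one-sided type I error 0.023. With a true −6 mmHg the estimate was −6.03 and power 0.82.

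**Does the proposed correction work?** Selection on baseline does not bias the regression of follow-up on baseline. Evaluating that regression at the mean baseline of everyone screened gave a change within 0.02 mmHg of zero, including when the limit was on awake SBP.

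**The case against.** - **The primary test is between arms and unbiased.** This stands. The point is confined to a secondary analysis in about 136 subjects.
- **The rule only grants a conclusion of no harm.** A reader might infer that failing it labels an arm as raising BP. Section 12.12.5 says no such thing. The bias makes the favourable conclusion harder to reach, so it cannot give false reassurance. The remaining harm is one of interpretation.
- **DBP and MAP.** A reader might infer that they carry the full artefact. They do not: the limit is on SBP, so they shift only through their correlation with it, and the 4 mmHg rule covers SBP alone.
- **The share excluded could be small.** The 40% also covers QC failures, atrial fibrillation, cuff fit, access arm, weight gain, unstable antihypertensives and the clinic SBP limit, some of which act first. At 2-5% excluded, the shift is half a millimetre of mercury or less. This stands, and the range has to include it.
- **Imprecision explains part of the failures.** True: without any artefact a neutral arm still misses the rule 17-21% of the time. Also, 54 per arm reflects the largest withdrawal allowed for.
- **The analysis plan may settle it.** Section 12.12.5 defers further considerations to the RAP, which is not at hand. The point is not that detail is missing: the protocol already fixes both the rule and the model, and together they give a biased value by default. If the RAP evaluates the mean elsewhere, the point falls away.

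**Conclusion.** The concern holds, limited to within-arm change in 24-hour SBP. One session serves as both an upper-only entry limit and the baseline, so the within-arm estimate is biased upward in both arms and the baseline covariate does not correct it.

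The direction follows from the protocol; the size does not. With an assumed baseline SD of 13-20 mmHg, the shift is about 0.15-0.5 mmHg at 2-5% excluded and 0.6-2.3 mmHg at 10-30%, slightly less once the awake/24-hour difference is allowed for. Against roughly 1 mmHg of room, the chance that a neutral arm meets the rule falls from 0.79-0.83 to 0.72-0.79 in the mild case, and to between 0.65 and 0.23 in the stronger one.

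The documents do not support reading this as a flaw in the sub-study's primary result, or as a route to wrongly clearing a drug. It is a known-direction bias in a key secondary conclusion that a small analysis change removes.

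**What to change.** In Section 12.12.5, add that the within-arm adjusted mean change in 24-hour SBP and its interval are also evaluated, from the same ANCOVA, at the mean baseline 24-hour SBP of all subjects with a valid baseline ABPM, including those excluded only by inclusion 7. Report this beside the uncorrected value and base the 4 mmHg conclusion on it.

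If the baseline readings of those excluded subjects were not retained, report the within-arm change descriptively with a regression-to-the-mean caveat, and rest the conclusion on the between-arm difference.

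The cost is a few lines of analysis-plan wording and one extra model evaluation. The downsides are a modest linear extrapolation above the cut-off, a somewhat wider interval, and reliance on screened subjects' baseline readings, whose retention the protocol does not state. Separating the qualifying session from the baseline session would be cleaner, but Section 9.2.3 says the study is fully enrolled, so an analysis change is the practical route.

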12.12.3.3. Study Assessments**Week -8 Study Visit:**

Subject's consent for ABPM is obtained (Note: if missed this may be obtained at Week -4 prior to ABPM assessments).

Week -4 Study Visit:

A baseline ABPM reading must be initiated at a mid-week dialysis visit and may be performed following completion of the Week -4 study assessments or at a subsequent mid-week dialysis visit provided it occurs at least 1 week prior to randomization.

Post-dialysis and prior to ABPM, subjects will be assessed for the presence of atrial fibrillation/flutter as follows: subjects with an irregular heart beat detected during heart rate measurement will undergo an ECG and those with documented atrial fibrillation or atrial flutter will not be eligible for ABPM.

The ABPM device will be placed on the arm opposite current vascular access, and will be removed by the subject at home after a minimum of 24 hours of wear; the device will be returned to the research staff at the next visit, which ideally is no later than 1 week prior to randomization to allow for QC of the ABPM. See SRM for guidance on placement of ABPM device.

If the subject fails to meet the baseline ABPM QC criteria and agrees to repeat the ABPM procedure, then:

- The baseline ABPM procedure can be repeated at the next mid-week dialysis visit. *Note: the atrial fibrillation/flutter assessment should be repeated prior to device placement.*
- Day 1 (randomization) may be delayed.
- If the baseline ABPM fails the QC criteria after three attempts, then the subject will not be enrolled in this ABPM sub-study.

Subjects will have their body weight measured and recorded in the eCRF both pre- and post-dialysis (see SRM for guidance on body weight measurement).

Day 1 (Randomization):

If the ABPM measurements meet the QC criteria, the subject can be randomized.

Subjects who either do not qualify for entry into the ABPM sub-study after failing QC criteria a third time or who do not desire to continue in the ABPM sub-study although they pass the QC criteria, should continue with randomization into the main study following the schedule of assessments as outlined in [Table 7](#) of the main protocol if appropriate.

Week 16 Study Visit:

At Week 16, at the mid-week dialysis visit and after all main study assessments have been completed, the subject's pre- and post-dialysis weight will be measured and the EDW will be recorded.

The ABPM device will be placed on the subject's arm by site personnel. After a minimum of 24 hours of wear, the device will be removed by the subject at home and returned to the research staff at the next visit. The time and date of study medication administration, before and while wearing the ABPM device, will be recorded.

If the ABPM fails the QC criteria (same as baseline), up to two additional attempts may be made at subsequent, mid-week dialysis visits. No further attempts are allowed. The subject will continue study visits in the main study as scheduled.

12.12.3.4. Permanent Discontinuation of Randomized Treatment

A subject who permanently discontinues randomized treatment prior to completing the ABPM sub-study should remain in the sub-study and complete the Week 16 ABPM assessment unless consent to participate in the ABPM sub-study is withdrawn (see also [Section 5.5](#)).

12.12.3.5. Estimated Dry Weight and Antihypertensive Medication Changes

It is preferred that no changes are made to EDW and antihypertensive medications while the subject is part of the sub-study.

If changes in EDW and/or antihypertensive medications are necessary, these must be documented in the eCRF along with the reasons. Subjects will remain in the sub-study regardless of any changes.

12.12.3.6. Withdrawal from ABPM Sub-Study

If a subject participating in this sub-study withdraws from the sub-study, the reason for the withdrawal must be recorded in the eCRF. The subject will remain in the main study unless the subject withdraws consent from the main study.

12.12.4. Sample Size and Power Calculations

The sample size of this sub-study has been designed based on the primary sub-study objective to demonstrate superiority in average SBP change from baseline to end of sub-study between arms (daprodustat versus rhEPO), measured by ABPM over a 24 hour assessment period. Assuming a one-sided 2.5% significance level, a true standard deviation for SBP change from baseline measured by ABPM of 11 mmHg [Peixoto, 2000], and up to a 20% withdrawal rate from the sub-study, a sample size of 68 subjects per group (136 subjects in total) will provide greater than 80% power to detect a -6 mmHg difference in treatment groups (i.e., achieve superiority). Under these assumptions, superiority will be established if there is more than a 4.2 mmHg mean difference observed in favor of daprodustat.

Assuming a 40% screen failure rate for the additional ABPM entry criteria, approximately 228 subjects that are eligible for the main study will need to be screened for the sub-study in order to randomize approximately 136 subjects. See Section 9.2.3 for more information about sample size adjustments.

Unblinded ABPM data will be reviewed by the IDMC during the conduct of the trial as part of their data monitoring responsibilities. No formal interim analysis is planned.

